7.3.2 Management of diabetes

The risk factors for diabetic retinopathy will be discussed with all participants at baseline and reviewed from time to time throughout the study. All participants will be informed that optimal control of blood glucose and blood pressure reduces the risk of loss of vision. Investigators will ensure that adequate arrangements are in place for the medical management of participants' diabetes, and will correspond in writing with the care providers at least at the baseline and closeout visits.

7.3.3 Recording AEs and SAEs

When an AE/SAE occurs, it is the responsibility of the investigator to review all documentation (e.g. hospital progress notes, laboratory, and diagnostic reports) relative to the event. The investigator/site staff will then record all relevant information regarding an AE/SAE in to the eCRF. Any SAE documentation forwarded to TGA/HREC will be de-identified maintaining patient anonymity. For each adverse event, start and stop dates, action taken, outcome, intensity (see Section 7.3.1) and relationship to study treatment and causality must be documented.

The investigator will attempt to establish a diagnosis of the event based on signs, symptoms, and/or other clinical information. In the absence of a diagnosis, the individual signs/symptoms should be documented.

8 Endpoints

8.1 Primary and Secondary Outcomes

Primary outcome:

- Reduction in high definition Spectral Domain Heidelberg Optical Coherence Tomography (OCT) subfield volume measurements at 8 weeks.

Secondary outcomes at 1 and 2 months:

- LogMAR VA
- Time to fluid reduction
- Time to oedema recurrence
- FFA assessment of leak and capillary closure before (at baseline) and after intervention (Week 5 and 16)
- Change in retinal sensitivity (dB) as measured by microperimetry from Baseline to week 1, week 5, week 8 and Week 16

Safety outcomes will be:

- Any loss of BCVA/VA
- Any increase in any OCT subfield

9 Statistical aspects of the study, safety and reporting

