Patients with diabetic macular oedema in one eye as defined by the eligibility criteria will receive thrice weekly 90 second treatments with NIR laser, supplied by Ellex, for 4 weeks. Twenty one patients will be sequentially allocated into three groups to receive laser doses 25, 100 or 200 mW/cm². The central 1 mm will be shielded so that the fovea will be protected in the event of any unanticipated toxic effect on the retina.

1.3.1 Primary outcome:

- Reduction in central macular thickness measured by optical coherence tomography at the conclusion of treatment and at 8 weeks compared with baseline.

1.3.2 Secondary outcomes:

- LogMAR Best Corrected Visual Acuity (BCVA)
- Time to oedema reduction
- Time to oedema recurrence
- FFA assessment of leak and capillary closure before (at baseline) and after intervention (week 5 and 16)
- Change in retinal sensitivity (dB) as measured by microperimetry from Baseline to Week 1, Week 5, Week 16 and 6 month follow up visit.

1.4 Power calculation:

This study is an exploratory study designed to provide estimates of outcomes for future studies, therefore power calculations have not been applied. Seven patients per group will be sufficient to produce these estimates and will give an indication of the effective dose range

1.5 Significance:

This study will shed light on whether a novel treatment that may complement existing treatments is safe and whether it warrants further investigation in a larger study

2 Research Plan

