2.2 Objective

This will be a 1 month exploratory study, with outcome measures assessments at 8 weeks and further assessment visit as 12 and 16 weeks, followed by a 6 month safety visit.

The specific aim of the study is to test the following hypothesis:

- That treatment with NIR light reduces diabetic macular oedema

Outcomes

Variables related to the progression or resolution of diabetic macular oedema will be serially examined in the study eye of all patients to determine the effects of NIR treatment. These are:

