2.2.1 Primary Outcome Measure at 8 weeks

Reduction in central macular thickness and total macular volume as measured by Spectral Domain Optical Coherence Tomography (OCT)

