2.2.2 Secondary Outcome measures at 1month, 8 weeks, 12 weeks and 16 weeks

- Best corrected LogMAR Visual Acuity (VA)
- Time to oedema reduction
- Time to oedema recurrence
- FFA assessment of leak and area of ischemia before and after intervention
- Change in retinal sensitivity (dB) as measured by microperimetry from Baseline to Week 5, 8, Week 16 and 6 month visit.

2.2.3 Safety outcomes will be:

- Any loss of VA
- Any increase in macular thickness as measured by OCT

3 Design

A cohort of 21 patients satisfying the inclusion criteria will be recruited from the outpatient hospital clinic. They will be sequentially allocated into one of three groups. Each group will have seven patients with group 1 enrolment completed first, followed by group 2 and finally, group 3. Each group will be managed identically but will receive a different dose of NIR energy.

Group 1 will be treated with a dose of 25 mW/cm² for 90 seconds (now fully enrolled)

Group 2 will be treated with a dose of 100 mW/cm² for 90 seconds (now fully enrolled)

Group 3 will be treated with a dose of 200 mW/cm² for 90 seconds.

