3.2 Organisational Structure of the Study Group

The centre will have trained BCVA examiners, a study coordinator, a photographer, an ophthalmologist performing the NIR laser light delivery, and an optical coherence tomography (OCT) examiner. There will be no masking in this study.

4 Participant Eligibility

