9.2 Statistical Analysis of OCT measurements

Retinal thickness measurements will be checked for artefacts. Only scans where the software was able to pick up the retinal thickness between the internal limiting membrane and the retinal pigment epithelium will be used.

The principal measurement of macular thickness will be the reading that appears in the central circle. Absolute change and percentage change in “abnormal thickness” will also be analysed in each subfield.

OCT measurements will be made and entered into the database.

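### The three statements of the primary outcome name different OCT measures, one adds a second time point, and nothing in the protocol decides between thickness and volume

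*Protocol*

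**What the plan says.** Three sections of the protocol are labelled as the primary outcome.

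- Section 1.3.1 (synopsis): "Reduction in central macular thickness measured by optical coherence tomography at the conclusion of treatment and at 8 weeks compared with baseline".
- Section 2.2.1, whose heading sets the time at 8 weeks: "Reduction in central macular thickness and total macular volume as measured by Spectral Domain Optical Coherence Tomography (OCT".
- Section 8.1 (Endpoints): "Reduction in high definition Spectral Domain Heidelberg Optical Coherence Tomography (OCT) subfield volume measurements at 8 weeks".

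Two other sections bear on the choice. Section 9.2 states: "The principal measurement of macular thickness will be the reading that appears in the central circle". It adds analyses of change in abnormal thickness by subfield and does not mention volume. Section 2.2 describes a one-month study "with outcome measures assessments at 8 weeks".

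On context, Section 1.4 says: "This study is an exploratory study designed to provide estimates of outcomes for future studies". Section 3.2 says: "There will be no masking in this study". Section 3 marks Group 1 as fully enrolled and says the same of Group 2: "Group 2 will be treated with a dose of 100 mW/cm² for 90 seconds (now fully enrolled". Section 2.1 already reports first-cohort results and suggests that a benefit may emerge after treatment has ended.

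**The concern.** A primary outcome should be one quantity at one time. Here a report could present central thickness, central thickness with total volume, or subfield volume as the primary result, and each choice would be faithful to some section of the protocol.

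The quantities are not interchangeable. Volume within a single fixed-area subfield carries the same information as its mean thickness, but Section 8.1 names no subfield, and total macular volume covers more retina than the centre. The difference matters in this trial because Section 6 describes a 4.5 mm beam with the central 1.0 mm masked. A central reading and a wider volume may therefore sample retina that was exposed differently.

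With no masking, no control group and some results already seen, the protocol gives no protection against choosing the measure or the time point once the data are known. The observation of a possible delayed effect bears directly on the choice between end of treatment and Week 8.

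**Working it through.** **Comparison of the definitions**

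| Candidate | 1.3.1 | 2.2.1 | 8.1 |
|---|---|---|---|
| Central thickness, end of treatment | yes | no | no |
| Central thickness, Week 8 | yes | yes | no |
| Total macular volume, Week 8 | no | yes | no |
| Subfield volume, Week 8 (subfield not named) | no | no | yes |

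There are four distinct candidates. One is shared by two sections (central thickness at Week 8) and none by all three. Week 8 appears in every definition, so the only conflict on time is the end-of-treatment assessment in Section 1.3.1.

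**Search for a rule that settles it**

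- Section 9.2 selects the central circle among thickness readings. It mentions neither volume nor the primary outcome.
- Section 3.1 lists subfield volume and thickness together without ranking them.
- Section 13.1 (OCT procedure) sends thickness map parameters to the outcome analysis and names no primary parameter.
- Section 2.2 supports Week 8 but is silent on the measure.

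**Device, a separate mismatch**

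Section 8.1 ties the outcome to Heidelberg. Section 5.2 allows a volume scan or a macula cube, and the OCT procedure also uses the Cirrus macula cube for outcome analysis. The autofluorescence procedure names Heidelberg as the maker of the Spectralis, which the OCT procedure lists separately from the Cirrus. Sections 1.3.1 and 2.2.1 name no maker, and nothing shows that any patient changed device.

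**Illustration of size**

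The protocol gives no alpha, efficacy test, SD or correlation, so there is no figure of its own to reproduce. The following are assumed: no true effect; normally distributed change scores; n = 7 per dose; one-sample t-tests at two-sided 5%, counting reductions only (t < −2.447, 6 df); one subfield for Section 8.1; 1,000,000 simulated replicates per setting (Monte Carlo SE at most 0.0003).

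For a single fixed outcome, the chance of a false significant reduction is 0.025 per dose group. Over three independent groups it is 1 − (1 − 0.025)³ = 0.073.

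| Rule for claiming a reduction | ρ = 0.5 | ρ = 0.7 | ρ = 0.9 | ρ = 0.99 |
|---|---|---|---|---|
| Any of the four readings | 0.082 | 0.071 | 0.051 | 0.033 |
| Any, leaving out total volume | 0.065 | 0.058 | 0.045 | 0.031 |
| Any of the three definitions, readings joined by 'and' both required | 0.029 | 0.031 | 0.031 | 0.027 |

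With ρ = 0.95 among Week 8 readings and 0.5 across visits, any of four gives 0.059 and the strict rule gives 0.029. At the upper end, over three groups, any of four gives 1 − (1 − 0.082)³ = 0.226.

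**The case against.** The best defence is that this is an exploratory study with no power calculation. No sample size, test or alpha depends on which OCT measure is primary, and every candidate comes from scans already scheduled, so all of them can be estimated and reported. The text also leans one way: Week 8 is in all three definitions, central thickness is in two, and Section 9.2 speaks only of thickness. On this view the matter is a wording repair of lower priority.

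The error-rate figures can be challenged too. They measure a decision that the protocol never makes. The largest needs a correlation of 0.5 even among same-visit scans, and it counts total volume alone although no section makes it primary alone. Read literally, the definitions give almost no inflation.

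Much of this stands. The figures are illustrative and cannot carry the point, and the device mismatch is a separate matter. But a lean in the text does not override Section 8.1, which is the formal Endpoints section and omits thickness. Nor is this a detail left to a statistical analysis plan: the protocol fixes the outcome three times, inconsistently, and a plan that chose one version would still contradict the others. Because the study exists to produce estimates, not knowing which estimate is the main one undermines its stated purpose.

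**Conclusion.** The contradiction is established from the text alone and must be corrected. The firm consequence is that the main estimate of the study is not identified and could be selected after results are known. The documents do not show that such selection took place.

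The effect on error ranges from slight to about threefold (0.082 / 0.025 = 3.3), depending on correlations the protocol does not give and on how the readings joined by 'and' are treated. No split of that effect between measure and time point is claimed.

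**What to change.** Write one primary measure at one time point, in identical words, in Sections 1.3.1, 2.2.1 and 8.1. List the remaining OCT measures and the end-of-treatment assessment as secondary. The option with most support is: *The primary outcome is the change from baseline to Week 8 in central-circle macular thickness on SD-OCT.* It is the only pair shared by two of the definitions, and it agrees with Section 9.2, with the Week 8 assessment in Section 2.2 and with the thickness criterion for eligibility in Section 4.2.1. If the sponsor prefers a volume because the centre of the beam is masked, name that single volume and align Section 9.2 with it.

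State which groups' outcome data (Group 1, and Group 2 if seen) were known when the definition was fixed. Reconcile Section 8.1 with Sections 5.2 and 13.1 on the device, keep each patient still to be enrolled on one device, and list the device used for scans already taken.

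The cost is a wording amendment. OCT is already scheduled at baseline, Week 5 and Week 8, so no visit or scan is added. There are three limits:

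- The amendment cannot make the outcome prespecified for data already seen, which is why the disclosure is needed.
- The sponsor gives up the option of a second primary OCT measure.
- If central thickness is chosen, the reading may largely sample retina that is not directly treated (the size of the central circle is not given), so the volumes should still be reported.

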9.1 Time Limits for Completing Study Visits

Due to the intensity of the visit schedule all patients will be selected based on their ability to maintain the intensive laser light therapy regimen. Should a laser visit be scheduled on a day which falls on a public holiday or similar all care should be made for the treatment visit to be administered on a day immediately before or after the scheduled treatment day taking into account weekends. All patients should be seen within two weeks of the safety follow up visits.

9.2 Statistical Analysis of OCT measurements

Retinal thickness measurements will be checked for artefacts. Only scans where the software was able to pick up the retinal thickness between the internal limiting membrane and the retinal pigment epithelium will be used.

The principal measurement of macular thickness will be the reading that appears in the central circle. Absolute change and percentage change in “abnormal thickness” will also be analysed in each subfield.

OCT measurements will be made and entered into the database.

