6.4 Rescue Treatment & Standard of Care

Patients with an increase of 100 microns in central macular thickness on OCT or a significant loss of vision (defined as a loss of 10 or more letters [2 lines] on a vision chart) at any stage in the study will

be discontinued from the study treatment and treated as per standard of care. Patients who are discontinued from the study and are treated with the standard of care during the study period will continue to be followed for the safety at the specified time points.

At the 16 week visit, patients will be assessed for the need for standard of care therapy according to each investigator's usual practice.

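### Using only OCT scans that segmented automatically makes missing values depend on something that may track retinal thickness, so the week-8 change can be biased toward benefit

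*Protocol*

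**What the plan says.** Protocol section 9.2 first states a check: "Retinal thickness measurements will be checked for artefacts". It then fixes which scans enter the analysis: "Only scans where the software was able to pick up the retinal thickness between the internal limiting membrane and the retinal pigment epithelium". No boundary correction and no repeat scan is mentioned, there or in the OCT procedure in section 13.1. Section 9.2 also names the main reading: "The principal measurement of macular thickness will be the reading that appears in the central circle".

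The OCT readings carry two outcomes:

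- **Primary.** Section 8.1 gives "Reduction in high definition Spectral Domain Heidelberg Optical Coherence Tomography (OCT) subfield volume measurements at 8 weeks". Section 2.2.1 also places the primary outcome at week 8, as central thickness and total volume. Section 1.3.1 adds the end of treatment and makes the comparison with baseline explicit.
- **Safety.** Section 8.1 lists "Any increase in any OCT subfield"; section 2.2.3 lists "Any increase in macular thickness as measured by OCT".

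Section 3 describes three dose groups of seven, all treated and enrolled one after another. Section 3.2 states that the study is not masked and lists an OCT examiner among the staff.

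**The concern.** This is an affirmative selection rule, not a detail left open for a later plan. An analysis plan that used hand-corrected scans would depart from the protocol as written.

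The rule selects on how the scan turned out, and the scan is the outcome. If segmentation fails more often in a thicker retina, an eye that worsens by week 8 is more likely to lose its week-8 value, and the eyes that remain look better than the whole group. Every group is treated and the effect is read as change from baseline, so no comparator shares and cancels the distortion. Section 1.4 says the study exists to supply estimates for later studies, so a shift in the estimate goes to its purpose.

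**Working it through.** The protocol gives no failure rate, standard deviation, effect size or power figure, so there is no stated figure to reproduce. What follows is a sensitivity check. Only the group size (7, section 3) and the entry threshold (above 300 microns, section 4.2.1) come from the documents; all other inputs are assumptions.

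**1. Chance of losing a week-8 scan.** One scan is 1/7 = 14% of a group. With failure rate p, the chance that at least one of n scans is lost is 1 − (1 − p)^n.

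| Assumed p | n = 7 | n = 21 |
|---|---|---|
| 5% | 1 − 0.95^7 = 30% | 66% |
| 10% | 1 − 0.90^7 = 52% | 89% |
| 20% | 1 − 0.80^7 = 79% | 99% |

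**2. Bias with a threshold failure rule.** Assume baseline thickness with mean 420 and SD 90 microns, true mean change 0, and change independent of baseline. At follow-up, failure is 2% at or below 450 microns and 10%, 20% or 40% above. By simulation, the mean change among usable scans is:

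- SD of change 60: about −1 to −6 microns.
- SD of change 100: about −2 to −13 or −14 microns.

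Restricting baseline to values above 300 microns moves the far end to just under −15. The share of rises above 100 microns still recorded at that one visit is about 91% down to 63%. This is close to one minus the assumed failure rate, so it adds little information of its own.

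**3. Bias with a graded failure rule.** Assume baseline above 300 microns (mean about 436, SD about 77), true mean change 0, overall failure of 5% to 20%, and a logistic slope of 1.5 per SD.

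| Failure depends on | Mean change, SD 40 | Mean change, SD 60 | Any increase (truth 50%) |
|---|---|---|---|
| nothing | 0 | 0 | 50% |
| baseline thickness only | 0 | 0 | 50% |
| week-8 thickness | −1.2 to −4.1 | −2.3 to −8.2 | 45% to 49% |
| the change itself | −2.6 to −9.1 | −3.9 to −13.6 | 41% to 48% |

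The last column is the share among usable scans.

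**4. Same thickness distribution at both visits.** Assume SD 80 at each visit, correlation 0.6 or 0.8 between visits, and about 10% failure per visit.

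- Failure at week 8 only: −3.8 (correlation 0.6) or −1.8 (0.8) microns.
- Failure at baseline only: +3.7 or +1.9 microns, against benefit.
- Same rule at both visits: 0.0, with about 17% of pairs lost.

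That cancellation needs equal distributions. In the model of step 2, thickness is more spread out at follow-up than at baseline, and applying the same rule at both visits leaves the bias almost unchanged.

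**5. Comparison with sampling error.** The standard error of a group mean is SD/√7: 40/√7 = 15, 60/√7 = 23 and 100/√7 = 38 microns. In step 2 the largest bias is 6/23 = 26% of a standard error at SD 60 and 14/38 = 37% at SD 100. In the least favourable row of step 3 it is 13.6/23 = 59%.

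**The case against.** Excluding a scan with failed boundaries has a sound purpose, because such a scan yields a wrong thickness. Fuller reading rules may sit in documents that are not shown. Both points are fair. The first argues against using the uncorrected number, not against correcting it; the second does not undo a rule that the protocol states outright.

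A reader might infer that the rule removes the most oedematous eyes and does bias the results toward benefit. The documents do not support that. They do not say how often segmentation fails or that it fails more in thick retinas. The rule drops scans, not patients. The direction depends on the mechanism, as steps 3 and 4 show. What can be said is that entry requires a measured thickness above 300 microns, which suggests a readable baseline scan in most enrolled eyes. Failure at follow-up, and so bias toward benefit, is then the more relevant case, though not an established one.

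A reader might also infer that a worsening eye vanishes from the safety count. Section 15 schedules ten OCTs after baseline (four Fridays, Monday and Tuesday of week 5, weeks 8, 12 and 16, and 6 months), so one lost scan does not remove an eye from an outcome of any increase. Vision loss is a parallel safety outcome. Nor do the documents count an unreadable scan as no increase; they leave its status unstated.

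The size is modest beside the sampling error of seven eyes in an exploratory study. That stands, but sampling error is visible in a confidence interval and selection is not.

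Finally, correction by hand in an unmasked study could bring its own bias. That stands and shapes the fix.

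**Conclusion.** The point holds as a possible bias that the protocol's own rule allows. OCT values go missing according to segmentation success. If failure rises with thickness at follow-up, the week-8 change is shifted toward benefit by about −1 to −14 microns under the assumed inputs, and some thickening is not recorded at that visit. The shift is zero if failure is unrelated to thickness, or if it acts alike at both visits with equal thickness distributions. It runs the other way if failure is mainly at baseline with regression to the mean.

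The exposure is greatest for the week-8 value, where one lost scan is 14% of a dose group and no control group absorbs the effect. It is weaker for the safety outcome, which has repeated scans. The remedy is a cheap improvement that should be made; nothing here shows that the results are wrong.

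**What to change.** In section 9.2, replace the discard rule with text along these lines:

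*Segmentation will be reviewed on every scan. Where the automatic boundaries are wrong or absent but the boundaries can be seen, the OCT examiner will correct them on a de-identified scan, without knowledge of visit or dose, and the corrected scan will be used. A scan will be excluded only if the boundaries cannot be seen. The numbers of corrected and excluded scans will be reported by visit and dose. For the OCT safety outcome, an excluded scan is recorded as unknown.*

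Section 3 reports the first two groups as fully enrolled, so the rule should be applied alike to all three groups, including scans already taken where these are retained.

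**Cost.** Minutes per failed scan, by an examiner already listed in section 3.2, and no additional scan. OCT scans must also be de-identified before correction: section 12.1 provides this for fundus photographs and angiograms, but no section provides it for OCT. Some reader subjectivity remains, and the reported counts let readers judge how much the result rests on corrected scans. The change assumes that the instrument software permits manual correction, which the documents do not say. If it does not, the counts by visit and dose and the unknown category for safety can still be adopted.
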